- iii. MTX: Subjects are permitted to continue MTX provided that the dose is stable for ≥ 12 weeks prior to randomization and remains stable throughout the study. Decrease in dose or discontinuation is permitted for AEs or intolerance.
- iv. Leflunomide (20 mg per day).
- v. Mycophenolate mofetil/mycophenolic acid (MMF). Note: Subjects who are receiving MMF may participate in the study only if administered as a maintenance therapy and up to a maximum of 2 g/day (or equivalent); in subjects of African ancestry, 3 g/day (or equivalent) is acceptable.
- vi. Dapsone (maximum 100 mg per day).
- c) Not applicable per Revised Protocol 03 CS (prednisone or equivalent) background therapy is permitted but not required. For subjects taking CS, the dose must be stable for ≥ 2 weeks before the screening visit, cannot exceed 40 mg/day at screening, and must remain stable until randomization. Further specifications are as follows:
 - O Topical and inhaled CS use is permitted but must follow a stable regimen throughout the study and cannot be used on an as-needed basis. Discontinuation of topical steroids should be allowed if lesions/rash resolve completely. Inhaled CS for nonlupus conditions will not count against the maximum CS dose.
 - o Patients are ineligible if they received intramuscular (IM), intra-articular (IA), intrabursal, IV, and modified-release CS use within 4 weeks prior to randomization.
- d) SOC that is allowed in this study must include at least one of the following:

Antimalarials, Immunosuppressants, or oral CS

Antimalarials and/or Immunosuppressants must have been taken for ≥ 12 weeks before the screening visit and must be at a stable dose for ≥ 8 weeks before the screening visit and remain stable until randomization and throughout study participation. Details for Antimalarials and/or Immunosuppressants are as follows:

• Antimalarials: chloroquine, HCQ, or quinacrine; monotherapy is permitted. Also see exclusion criteria below regarding HCQ dose limitation and exclusionary screening HCQ levels. Subjects on HCQ must have an ophthalmology assessment within

6 months prior to randomization, confirming no findings of HCQ induced retinal toxicity.

- Immunosuppressants (combinations of these are NOT permitted):
 - o Azathioprine (maximum 200 mg per day).
 - o 6-mercaptopurine (6-MP, maximum 1.5 mg/kg per day).
 - MTX: Subjects are permitted to continue MTX provided that the dose is stable for

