 ≥ 12 weeks prior to randomization and remains stable throughout the study.
 Decrease in dose or discontinuation is permitted for AEs or intolerance.
 - o Leflunomide (20 mg per day).
 - o Mycophenolate mofetil/mycophenolic acid (MMF). Note: Subjects who are receiving MMF may participate in the study only if administered as a maintenance therapy and up to a maximum of 2 g/day (or equivalent); in subjects of African ancestry, 3 g/day (or equivalent) is acceptable.
 - O Dapsone (maximum 100 mg per day).
- e) CS (prednisone or equivalent), as follows:
 - o For subjects taking oral CS as monotherapy, CS must have been taken for ≥ 6 weeks prior to the screening visit at a dose ≥ 7.5 mg/day and ≤ 40 mg/day prednisone (or prednisone equivalent), must be at a stable dose for ≥ 2 weeks prior to the screening visit and remain stable until randomization.
 - For subjects taking oral CS not as monotherapy, the CS dose must be stable for ≥2 weeks before the screening visit, cannot exceed 40 mg/day at screening, and must remain stable until randomization.
 - O Topical and inhaled CS use is permitted but must follow a stable regimen throughout the study and cannot be used on an as-needed basis. Discontinuation of topical steroids should be allowed if lesions/rash resolve completely. Inhaled CS for nonlupus conditions will not count against the maximum CS dose.
 - Subjects are ineligible if they received IM, IA, intrabursal, IV, and modified-release
 CS use within 4 weeks prior to randomization.

5) Other Inclusion Criteria: SLE Sub-protocol

a) Subject re-enrollment (rescreening): This study permits the re-enrollment of a subject who has discontinued the study as a pretreatment (screening) failure (ie, subject has not been randomized/has not been treated). If re-enrolled, the subject must be re-consented.

Clinical Protocol
BMS-986195
IM014029 - SLE
Branebrutinib

SLE 5.2 Exclusion Criteria

An individual who meets any of the following criteria will be excluded from participation in the SLE sub-protocol:

1) General Medical Conditions and History: SLE Sub-protocol

- a) Any major illness/condition or evidence of an unstable clinical condition (eg, renal, hepatic, hematologic, gastrointestinal, endocrine, pulmonary, immunologic, psychiatric) or local active infection/infectious illness that, in the investigator's judgment, will substantially increase the risk to the subject if he or she participates in the study.

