- x) Administration of all live vaccines is prohibited within 90 days before randomization. Administration of inactivated vaccines and nonlive vaccines, including those for influenza and SARS-CoV-2, is prohibited within 30 days before randomization. See SLE Table 6 for corresponding on-treatment and posttreatment restrictions.
- y) Treatment with DMARDs (excluding HCQ) or immunomodulators beyond required washout period before randomization; MTX treatment within 12 weeks before randomization or during the study. **HCQ whole blood concentration** > 2 μg/mL (at screening only) is exclusionary. HCQ dose > 400 mg/day, new initiation, or dose increases during treatment are not permitted.
- 6) Physical and Laboratory Test Findings: SLE Sub-protocol
 - a) Clinically significant abnormalities on chest x-ray or ECG

Clinical Protocol BMS-986195

- b) Clinically significant abnormalities in laboratory tests including the following:
 - i. Serum alanine aminotransferase (ALT) $> 2 \times ULN$
 - ii. Serum aspartate aminotransferase (AST) > 2× ULN
 - iii. Serum total bilirubin > 1.5× ULN (does not apply to subjects with Gilbert's syndrome)
 - iv. Hemoglobin < 8 g/dL (< 80 g/L) or, if due to hemolytic anemia related to SLE, < 7 g/dL (< 70 g/L)
 - v. Proteinuria > 3.0 g/day (> 3,000 mg/day) or equivalent level of proteinuria as assessed by UPCR (3 mg/mg or 339 mg/mmol)
 - vi. Estimated glomerular filtration rate (eGFR) < 50 mL/min/1.73 m² as calculated by the central laboratory
 - vii. Serum creatinine > 2.0 mg/dL (> 177 μmol/L)
 - viii. Absolute WBC count $< 2.5 \times 10^3 / \mu L$ ($< 2.5 \times 10^9 / L$)
 - ix. Neutrophil count $< 1000/\mu L$ ($< 1.0 \times 10^9/L$)
 - x. Platelet count $< 75 \times 10^3 / \mu L$ ($< 75 \times 10^9 / L$), if considered part of SLE disease activity without increased risk of bleeding
- c) Any other significant laboratory or procedure abnormalities that, in the opinion of the investigator, might pose unacceptable risk to the subject during the study
- d) Blood pressure (BP) > Grade 1 hypertension (> 159 mmHg systolic and > 99 mmHg diastolic) according to the 2018 ESC/ESH Guidelines for the management of arterial hypertension.
- e) The following exclusionary ECG observations:
 - i. QT interval with Fridericia's correction (QTcF): > 480 msec
 - ii. QRS: > 120 msec
 - iii. Complete heart block
 - iv. Left bundle branch block
 - v. Mobitz II second-degree atrioventricular block
 - vi. Atrial fibrillation or flutter

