	Topical and inhaled CS	allowed if lesions/rash resolve	Not applicable
		completely. Inhaled CS for	
		nonlupus conditions will not	
		count against the maximum CS	
		dose	
		Must have been taken for ≥ 12	
		weeks before the screening visit	
		and must be at a stable dose for	10 1 10
A	Chl	\geq 8 weeks before the screening	12 weeks if not
Antimalarial drugs	Chloroquine and quinacrine	visit and remain stable until randomization and throughout	continuing as background SOC
		study participation. New	background SOC
		initiation or change in dose	
		during treatment is not permitted	
		Doses of > 400 mg/day are not	
		permitted	12 weeks if not
	Hydroxychloroquine (HCQ)	New initiation or dose increase	continuing as
		during treatment is not	background SOC
		permitted. Whole blood levels at	G 2 2 3
		screening must be $\leq 2 \mu g/mL$ Treatment with anticoagulant or	
		antiplatelet therapies, including	
Anticoagulant or	Anticoagulant or antiplatelet	aspirin for cardioprotection,	
Antiplatelet therapies	therapies, including aspirin	within 2 weeks prior to	2 weeks
	for cardioprotection	randomization or during the	
		study	

Protocol Amendment No.: 04

Date: 01-Dec-2021 78

SLE Table 6 Prohibited and Restricted Medications

Type of Medication	Examples of Medications	Restrictions	Required Washout Period Prior to and Postrandomization
Anti-TNF therapy	Adalimumab, certolizumab, etanercept, golimumab, infliximab, and TNF biosimilars	Prohibited during the study	3 months
Biologics	Rituximab	Prohibited during the study	12 months
	Belimumab	Prohibited during the study	6 months
	Abatacept	Prohibited during the study	6 months
	Other Biologics, including tocilizumab, anakinra		8 weeks
	IVIG	Prohibited during the study	8 weeks
Immunosuppressants (allowed) Note: combinations of immunosuppressants are not allowed	Azathioprine, 6-MP, MTX, leflunomide, MMF	Must have been taken for ≥ 12 weeks before the screening visit and must be at a stable dose for ≥ 8 weeks before the screening visit and remain stable until randomization and throughout study participation. New initiation or dose changes during treatment are not permitted.	12 weeks if not continuing as background SOC, except leflunomide 36 weeks before screening
Immunosuppressants (prohibited)	Cyclosporine, tacrolimus, thalidomide and similar (oral); topical calcineurin inhibitors (tacrolimus, pimecrolimus)	Prohibited during the study	8 weeks
O.I. D.M.D.	Cyclophosphamide	Prohibited during the study	24 weeks

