Chronic medications, such as statins and antidepressants, that could be sensitive to the modulation of CYP2C8/P-gp, (and other potentially relevant drug metabolizing enzymes that may lead to drug-drug interaction with branebrutinib) and with sufficient representation in the study population (eg, > 10% per sub-protocol) are allowed in the study for accompanying conditions. For optional measurement of the concentrations of these medications, PK samples will be collected predose and 2 hours postdose at Week 0 (Day 1) and Week 4 (Day 29) for potential post-hoc analysis. These analyses will be based on the totality of information about the frequency of use of the drugs, clinical manifestations of possible interactions, availability of validated bioanalytical assays and therapeutic index. When performed, the results of these analyses, will be reported separately, along with the reasons for the selection. Concentrations of HCQ will also be measured and reported.

The dosing of allowed chronic medications must be maintained at the same level throughout the study unless safety concerns arise. Any changes of dose will be recorded, and additional PK sampling may be performed as a result.

Tobacco use will be allowed in the study. Branebrutinib concentrations will be compared between smoking and nonsmoking subgroups to evaluate the effect of smoking on glutathione-s-transferase mediated metabolism of branebrutinib.

No new concomitant medications (prescription, over-the-counter, or herbal) are to be administered during the study unless they are prescribed for treatment of specific clinical events. Any concomitant therapies must be recorded on the eCRF.

Clinical Protocol
BMS-986195
IM014029 - SLE
Branebrutinib

For subjects on immunosuppressant background therapy, the investigator must refer to the label for any potential interaction with concomitant medications:

SLE 6.7.2 Oral Corticosteroid Taper or Rescue for SLE Flare

Oral CS taper is detailed in Section SLE 8.1.1.10.

A maximum of 1 burst of oral CS rescue therapy is permitted in response to increased SLE disease activity up to Week 12 during the treatment period at the investigator's discretion.

- Rescue therapy must not exceed 40 mg/day prednisone or equivalent and must return within 10 days to the previous CS dose used before initiation of rescue therapy.
- Rescue therapy other than prednisone or equivalent is not permitted.

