If a subject requires CS rescue therapy after the first 12 weeks, the subject will be considered a nonresponder for analysis purposes but will continue to receive study treatment.

SLE 6.7.3 Other Restrictions and Precautions

No other restrictions and precautions have been identified.

SLE 6.8 Treatment After the End of the Study

At the end of the study, BMS will not continue to provide BMS-supplied study treatment to subjects/investigators unless BMS chooses to extend the study. The investigator should ensure that the subject receives appropriate SOC to treat the condition under study.

SLE 7 DISCONTINUATION CRITERIA

SLE 7.1 Discontinuation from Study Treatment

SLE 7.1.1 Permanent Discontinuation from Study Treatment

Subjects MUST discontinue study treatment (and non-IP at the discretion of the investigator) for any of the following reasons:

- A subject requests to stop study treatment Subjects who request to discontinue study
 treatment will remain in the study and must continue to be followed for protocol-specified
 follow-up procedures. The only exception to this is when a subject specifically withdraws
 consent for any further contact with him/her or persons previously authorized by the subject to
 provide this information.
- Any clinical AE, laboratory abnormality, or intercurrent illness which, in the opinion of the
 investigator, indicates that continued participation in the study is not in the best interest of the
 subject; if treatment is discontinued due to an AE, the AE eCRF must be completed to show
 that the AE caused discontinuation.
- Termination of the study program by BMS.
- Loss of ability to freely provide consent through imprisonment or involuntary incarceration for treatment of either a psychiatric or physical (eg, infectious disease) illness.

- Unblinding of a subject's treatment assignment for any reason (emergency or nonemergency).
- Inability or failure to comply with protocol requirements.
- Pregnancy.

Discontinuation of the study treatment should be considered by the investigator for abnormal liver tests indicative of drug-induced liver injury (DILI; see Section SLE 8.2.8 for definition) when the DILI meets one of the conditions necessary to be defined as an SAE outlined in APPENDIX 3, or if the investigator believes that discontinuation is in the best interest of the subject.

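### The SLE sub-protocol gives incompatible rules for background methotrexate and leaves safety-driven dose changes of the other allowed immunosuppressants unclear, with an unstated route to the primary endpoint

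*Combined protocol and SAP*

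**What the plan says.** All of the passages below are current text in the SLE sub-protocol.

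- **SLE 5.1, inclusion 4d.** Antimalarials and immunosuppressants must be at a stable dose throughout participation. The MTX entry lets subjects stay on it at a stable dose and adds: "Decrease in dose or discontinuation is permitted for AEs or intolerance". Azathioprine, 6-MP, leflunomide, MMF and dapsone appear in the same list without such a sentence.
- **SLE 6.7.1, SLE Table 6, allowed immunosuppressants.** The row names azathioprine, 6-MP, MTX, leflunomide and MMF, and states: "New initiation or dose changes during treatment are not permitted". Dapsone has its own row with the same bar. Neither row has an exception for AEs.
- **SLE 5.2, exclusion 5y.** Among the exclusionary items is "MTX treatment within 12 weeks before randomization or during the study".
- **SLE 6.7.1, text after Table 6.** "The dosing of allowed chronic medications must be maintained at the same level throughout the study unless safety concerns arise". The paragraph before it concerns drugs such as statins and antidepressants taken for accompanying conditions.
- **SLE 7.1.1.** "Subjects MUST discontinue study treatment (and non-IP at the discretion of the investigator) for any of the following reasons"; one of the reasons is "Inability or failure to comply with protocol requirements".
- **SLE 9.4.1.** Binary endpoints are imputed as nonresponse after early discontinuation of study treatment, after a prohibited medication is started, or when endpoint data are missing.

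**The concern.** An investigator whose subject has an AE on background MTX finds one passage that permits a reduction, one that forbids any change, and one under which the subject should not be on MTX at all. For the other listed drugs there is a bar on changes and a safety exception of uncertain reach.

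The statistical interest lies in what follows. If the change is permitted, the subject stays on study drug and contributes a Week 24 outcome. If it is taken as failure to comply, SLE 7.1.1 makes stopping study drug mandatory, and the primary endpoint is set to nonresponse. SLE 7.1.1 then calls for an end-of-treatment visit as soon as possible and a safety visit about 4 weeks later, and SLE 7.1.3 ends follow-up there. For an early stop, the on-schedule Week 24 assessment would not be collected, and no later sensitivity analysis could recover it.

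Safety handling is affected too, because sites need to know which rule governs. Immunosuppressant use is the randomization stratification factor, so subjects on these drugs are expected by design.

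**Working it through.** **1. The rules side by side**

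| Drug | Inclusion 4d | Table 6 | Exclusion 5y | Safety sentence in 6.7.1 |
|---|---|---|---|---|
| MTX | Allowed; may be lowered or stopped for AEs or intolerance | Allowed; no dose change | Exclusionary within 12 weeks before randomization or during the study | Reach unclear |
| Azathioprine, 6-MP, leflunomide, MMF | Allowed; stable; no AE exception | Allowed; no dose change | Not named | Reach unclear |
| Dapsone | Allowed; stable; no AE exception | Allowed (separate row); no dose change | Not named | Reach unclear |

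For MTX the three middle columns cannot all hold.

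**2. Is an exception implied in Table 6?** The table words its limits differently from row to row. The hydroxychloroquine row bars initiation and dose increases only, and the topical corticosteroid row expressly allows discontinuation when lesions clear. The immunosuppressant and dapsone rows bar changes in either direction. The introduction to Table 6 also refers the reader to SLE 5.2 for details, which is where 5y stands, and not to 4d in SLE 5.1.

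**3. From a dose change to the endpoint.** A reduction of a background drug is not early discontinuation of study treatment, not the start of a prohibited medication and not missing data, so it triggers no imputation under SLE 9.4.1. The route needs two further steps: the change is classed as failure to comply, and study drug is then stopped under SLE 7.1.1. The documents neither make nor exclude the first step. By contrast, SLE 6.7.2 says what happens after corticosteroid rescue later than Week 12: nonresponder, study treatment continues. No such statement covers a safety-driven change in an immunosuppressant.

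**4. Scale of one recoded responder.** SLE 9.1 plans 45 subjects on branebrutinib and 15 on placebo.

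- Branebrutinib: 1/45 = 2.2 points.
- Placebo: 1/15 = 6.7 points.

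To set this against the plan's own figure, SLE 9.1 expects a 95% CI of 2% to 56%. With d = p1 − p0, the unpooled interval is d ± 1.96 × √[p1(1 − p1)/45 + p0(1 − p0)/15]. Whole-number counts of 25/45 and 4/15 reproduce it:

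- d = 55.6% − 26.7% = 28.9%; SE = √(0.00549 + 0.01304) = 0.136; CI 2.2% to 55.6%.

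These counts are inferred. The stated rates of 55% and 30% put into the same formula give −2.4% to 52.4%, which is a separate matter. Starting from the inferred counts:

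- One branebrutinib responder recoded: 24/45 vs 4/15, d = 26.7%, CI −0.0% to 53.4%.
- One placebo responder recoded: 25/45 vs 3/15, d = 35.6%, CI 10.6% to 60.5%.

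A shift occurs only if the recoded subject would otherwise have been a responder.

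**The case against.** The strongest reply is that SLE 6.7.1 already answers the question. Right after Table 6 it says doses of allowed chronic medications "must be maintained at the same level throughout the study unless safety concerns arise", and that changes are recorded. If background immunosuppressants count as such medications, Table 6 does not forbid a safety reduction. Inclusion 4d can also be read as the drug-specific exception to a grouped table row. Exclusion 5y might be meant only for subjects who are not continuing MTX, since Table 6 gives a 12-week washout for them. SLE 8 sends immediate safety concerns to the Medical Monitor, which makes opposite handling at different sites less likely. Finally, the full analysis set is primary, the per-protocol set is only possibly supportive, and it excludes only statistically relevant deviations.

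Part of this stands. The readings are possible, central contact reduces divergence, and the per-protocol consequence is minor. But none of the readings is stated. The safety sentence follows a paragraph about drugs for other conditions. The 4d exception names MTX alone, so it does not help the other drugs. Exclusion 5y carries no qualifier, and its words about treatment during the study cannot be squared with continued MTX.

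A reader might infer that lowering a background drug itself makes the subject a nonresponder. SLE 9.4.1 does not say that.

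**Conclusion.** The point holds as an internal inconsistency. For MTX, inclusion 4d, Table 6 and exclusion 5y conflict. For the other allowed immunosuppressants and dapsone, the reach of the safety exception is unclear. The effect on the primary endpoint is conditional: it arises only if a change is treated as failure to comply and study drug is then stopped.

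The size per subject is 2.2 points on branebrutinib or 6.7 points on placebo, assuming the planned arm sizes and a subject who would otherwise have responded. The total cannot be given, because the documents state neither how many subjects will take these drugs nor how many will need a change.

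A reader might also infer a bias in a particular direction, for example that reductions would be more frequent on branebrutinib. The documents give no reduction rates by arm and no basis for that claim. Of the drugs in the Table 6 immunosuppressant row, only mycophenolate appears in the Master Protocol's interaction table; MTX does not. The direction is unknown.

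The correction is still worth making, because it concerns safety handling and possibly the primary endpoint in a comparison with 15 placebo subjects.

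**What to change.** 1. Reconcile inclusion 4d, exclusion 5y, the immunosuppressant and dapsone rows of SLE Table 6, and the safety sentence in SLE 6.7.1, so that one rule applies to each listed drug. The clinical rule is for the sponsor to choose.
2. In SLE 9.4.1 or the SAP, before database lock, state whether a background dose change made under that rule counts as noncompliance under SLE 7.1.1, as nonresponse for binary endpoints, or as grounds for exclusion from the per-protocol set.

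The cost is a few lines of protocol text in these places and a short analysis statement. No new data collection is needed and the sample size does not change.
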